3.2.3 Sensitivity analysis

- The primary estimand will be analyzed using a MMRM, under the missing at random framework. The model will include treatment, previous OADs, visit (Week 8, Week 12 and Week 18), treatment-by-visit interaction as fixed effects, and baseline HbA1c value-by-visit interaction as continuous covariate. The randomization stratum of HbA1c will be removed from the MMRM model given that the baseline HbA1c value is already in the model. The MMRM model will be implemented using SAS® (Version 9.4 or higher) MIXED procedure (PROC MIXED) with an unstructured correlation matrix to model the

within-participant errors. Parameters will be estimated using the restricted maximum likelihood method with the Newton-Raphson algorithm. Denominator degree of freedom will be estimated using the Kenward-Roger approximation by fitting values from post-randomization visits. LS Means difference between treatments, SE, 2-sided 95% CI, and 2-sided non-inferiority p-value from MMRM will be provided.

- The analysis of primary estimand will be repeated under a penalized multiple imputation strategy based on ITT population. The imputed HbA1c value at Week 24 in the iGlarLixi group will be penalized by adding 0.3% (corresponding to the non-inferiority margin), whereas the imputed HbA1c in the IDegAsp group will not be penalized.

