Missing HbA1c values will be imputed 1000 times to generate 1000 datasets with complete HbA1c values using SAS procedure for multiple imputation (PROC MI). The imputation model will include the treatment group, as fixed effect, and baseline HbA1c continuous value as covariate. The randomization strata of HbA1c can be removed from the model given that the baseline HbA1c continuous value is already in the model.

For each of the 1000 imputed datasets, the change in HbA1c from baseline to Week 24 will be analyzed using an ANCOVA with treatment groups and previous OADs as fixed effects, and baseline HbA1c continuous value as covariate. The results obtained from analyzing the datasets will be combined using Rubin's rule to draw inference. The non-inferiority will be assessed using the upper bound of the 2-sided 95% confidence interval (CI). If the upper bound of the 95% CI is less than 0.3%, the non-inferiority of iGlarLixi versus IDegAsp will be claimed.

Sensitivity analyses of primary estimand

The following sensitivity analyses will be performed for the primary estimand.

- The primary endpoint will be analyzed using a mixed-effect model with repeated measures (MMRM), under the missing at random framework. The model will include treatment, previous OADs, visit, treatment-by-visit interaction as fixed effects, and baseline HbA1c value as continuous covariate. The randomization strata of HbA1c can be removed from the MMRM model given that the baseline HbA1c value is already in the model. The MMRM model will be implemented using SAS® (Version 9.4 or higher) MIXED procedure (PROC MIXED) with an unstructured correlation matrix to model the within-participant errors. Parameters will be estimated using the restricted maximum likelihood method with the Newton-Raphson algorithm. Denominator degree of freedom will be estimated using the Kenward-Roger approximation by fitting values from post-randomization scheduled visits.

Primary analysis for the secondary estimands

Under hypothetical strategy, measurements after treatment discontinuation and/or initiation of rescue medication will be considered as missing data.

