3.2 PRIMARY ENDPOINT(S) ANALYSIS

3.2.1 Definition of endpoint(s)

The primary endpoint is the absolute change from baseline to week 24 in HbA1c. All the efficacy assessments collected during the study will be used, including those obtained after treatment discontinuation or initiation of rescue therapy (refer to [Section 5.5](#) for definition).

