 - For participants discontinuing prematurely the treatment, the missing HbA1c values will be imputed using data from participants also discontinuing treatment but having their HbA1c assessment (retrieved dropouts). In case there are not enough observed Week 24 data post treatment discontinuation, ie, less than 10 in either arm, or the model does not converge, whichever happens, return-to-baseline (RTB) approach will be used for imputation; missing HbA1c values at Week 24 will be imputed from a normal distribution with the expected value set to the participant's baseline value and standard deviation based on the baseline value by treatment group.

Missing HbA1c values will be imputed 1000 times to generate 1000 datasets with complete HbA1c values using SAS procedure for multiple imputation (PROC MI). The imputation model will include the treatment group as fixed effect, and baseline, Week 8, Week 12 and Week 18 HbA1c continuous value as covariate. The randomization stratum of HbA1c can be removed from the model given that the baseline HbA1c continuous value is already in the model.

For each of the 1000 imputed datasets, the change in HbA1c from baseline to Week 24 will be analyzed using an ANCOVA with treatment groups and previous OADs as fixed effects, and baseline HbA1c continuous value as covariate. The results obtained from analyzing the datasets will be combined using Rubin's rule to draw inference.

The non-inferiority will be assessed using the upper bound of the 2-sided 95% confidence interval (CI). If the upper bound of the 95% CI is less than 0.3%, the non-inferiority of iGlarLixi versus IDegAsp will be claimed.

Descriptive statistics for HbA1c results and changes from baseline will be provided for baseline and each visit by treatment group. Mean changes from baseline with the corresponding standard error will be plotted over time.

Missing data assumption check

The following analyses will be performed on the ITT population to explore the missing data frequency and pattern in the primary efficacy analysis:

- To explore missing data patterns for HbA1c in the primary efficacy analysis, number (%) of participants and number (%) of participants by baseline characteristics will be presented by the following missing data pattern and by treatment group. Descriptive statistics and plots for HbA1c results and changes from baseline will be provided by missing data pattern and by treatment group:

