3.2.4 Supplementary analyses

Secondary estimand 1

Under hypothetical strategy, measurements after treatment discontinuation and/or initiation of rescue medication will be considered as missing data.

A MMRM, under the missing at random framework, will be performed based on ITT population. The model will include treatment, previous OADs, visit (Week 8, Week 12, Week 18 and Week 24), treatment-by-visit interaction as fixed effects, baseline HbA1c value-by-visit interaction as continuous covariate. The randomization stratum of HbA1c will be removed from the MMRM model given that the baseline HbA1c continuous value is already in the model. The MMRM model will be implemented using SAS® (Version 9.4 or higher) MIXED procedure (PROC MIXED) with an unstructured correlation matrix to model the within-participant errors. Parameters will be estimated using the restricted maximum likelihood method with the Newton-Raphson algorithm. Denominator degree of freedom will be estimated using the Kenward-Roger approximation by fitting values from post-randomization scheduled visits. LS Means difference between treatments, SE, 2-sided 95% CI, and 2-sided nominal non-inferiority p-value from MMRM will be provided.

Secondary estimand 2

For the per protocol estimand, the change in HbA1c from baseline to Week 24 will be analyzed using an ANCOVA with treatment group and previous OADs as fixed effects, and baseline HbA1c continuous value as covariate. Provided that participants with treatment discontinuation or rescue medication, as well of participants with missing assessment will be excluded from PP population, no missing data handling method is planned for this analysis. LS Means difference between treatments, SE, 2-sided 95% CI, and 2-sided nominal non-inferiority p-value from ANCOVA will be provided.

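### The MMRM sensitivity analysis of the primary estimand (SAP 3.2.3) leaves Week 24 out of its visit factor, so it cannot estimate the Week 24 HbA1c difference it is meant to check

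*SAP*

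**What the plan says.** SAP 3.2.1 defines the target: "The primary endpoint is the absolute change from baseline to week 24 in HbA1c". SAP 3.2.3 then sets out the first of two sensitivity analyses: "The primary estimand will be analyzed using a MMRM, under the missing at random framework". Its fixed effects include "visit (Week 8, Week 12 and Week 18), treatment-by-visit interaction as fixed effects", and baseline HbA1c enters by visit. The output is "LS Means difference between treatments, SE, 2-sided 95% CI, and 2-sided non-inferiority p-value from MMRM will be provided", with no week named.

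Three other places bear on this:

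- SAP 3.2.4, the MMRM for secondary estimand 1 (hypothetical strategy), has the same structure but lists "visit (Week 8, Week 12, Week 18 and Week 24), treatment-by-visit interaction as fixed effects".
- SAP 3.2.2, the imputation model for the primary analysis, uses "baseline, Week 8, Week 12 and Week 18 HbA1c continuous value as covariate".
- Protocol 9.3.2 describes the same sensitivity MMRM without restricting the visits: "The model will include treatment, previous OADs, visit, treatment-by-visit interaction as fixed effects".

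**The concern.** A repeated-measures model gives treatment differences only at the visits it contains. With Weeks 8, 12 and 18 as the only levels, there is no Week 24 intercept, treatment effect or baseline slope, and so no Week 24 LS mean. The SAP still asks for a non-inferiority p-value from this model. Taken literally, that p-value could refer only to Week 18, an earlier visit, or an average over visits.

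The role of this analysis makes that more than cosmetic. It is the only sensitivity analysis that the protocol itself spells out for the primary estimand. The SAP adds one more, the penalised imputation, which reuses the primary imputation and adds 0.3% to imputed iGlarLixi values. The MMRM is therefore the only treatment-policy check that does not depend on that imputation.

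Week 18 is also a poor stand-in for Week 24. Protocol 6.8.4 triggers the rescue assessment on HbA1c above 8% at Week 12 or later, with a possible retest four weeks on (Week 16 at the earliest in that case). Protocol 3.1 describes HbA1c as reflecting the previous 2 to 3 months. Much of the effect of rescue, which a treatment-policy estimand is meant to capture, could appear only after Week 18.

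**Working it through.** **Inputs**

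- Visit levels in the sensitivity MMRM: Weeks 8, 12, 18 (SAP 3.2.3).
- Visit levels in the parallel MMRM: Weeks 8, 12, 18, 24 (SAP 3.2.4).
- Fixed effects in both: treatment, previous OADs, visit, treatment-by-visit, baseline-by-visit.
- Planning figures: 290 per arm, SD 1.05%, margin 0.3%, true difference 0, two-sided 0.05, 90% power, 10% dropout (SAP 4).

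**The plan's sample size, as background.** Per arm, n = 2 × (1.960 + 1.282)² × 1.05² / 0.3² = 257.5, rounded up to 258. Allowing for dropout, 258 / 0.9 = 286.7, rounded up to 287 per arm, or 574 in total. The t-test version needs 259 per arm; 259 / 0.9 = 287.8, so 288 per arm and 576 in total. The stated 580 is reproduced closely. The concern does not rest on it.

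**Is the Week 24 contrast estimable?** A contrast is estimable if adding it as a row to the design matrix leaves the rank unchanged. Taking previous OADs as two levels, the rank is one for OAD plus one per visit for each of visit, treatment-by-visit and baseline-by-visit.

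| Visits fitted | Rank of design | Rank with Week 24 contrast added | Week 24 difference |
|---|---|---|---|
| 8, 12, 18 | 1 + 3 × 3 = 10 | 11 | not estimable |
| 8, 12, 18, 24 | 1 + 3 × 4 = 13 | 13 | estimable |

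The latest contrast that the model in SAP 3.2.3 can estimate is Week 18.

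**Does anything else bring Week 24 in?**

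1. The list cannot be read as illustrative. HbA1c is also measured at Week 4 (protocol 1.3; SAP Table 7), and both SAP lists omit it. The parentheses define which visits are fitted.
2. Week 24 values cannot enter under another label. SAP Table 7 assigns study days 105 to 146 to Week 18 and day 147 onward to Week 24.
3. The degrees-of-freedom sentence, "Kenward-Roger approximation by fitting values from post-randomization visits", adds no level to the visit factor.
4. The three weeks match the post-baseline covariates of the imputation model in SAP 3.2.2. There, leaving out Week 24 is right, because Week 24 is the value being imputed. The list may have been carried over from there, but that is inference and the finding does not need it.

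**Size of the omission.** Treating the 10% dropout as the proportion without a Week 24 value, 290 × 0.9 = 261 per arm and 2 × 261 = 522 values would not be used by this model.

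**The case against.** The strongest reply is that the intended target is not in doubt. SAP 3.2.3 says it analyses the primary estimand, which is defined at Week 24; the protocol's version has an unrestricted visit factor fitted to scheduled post-randomisation visits; and the SAP declares no major changes from the protocol. A programmer would find that the requested contrast does not exist and would query it. The model also carries no alpha: the non-inferiority claim depends only on the ANCOVA with multiple imputation, and the hierarchical testing procedure covers only primary analyses of primary estimands. Other Week 24 analyses remain, namely the penalised imputation, the hypothetical-estimand MMRM and the per-protocol ANCOVA.

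Most of this stands, and it limits the consequence. The primary decision is safe and the cause is very probably a slip. The figure of 522 is also only a planning count. Participants who stop study drug are to be followed to scheduled completion, so the number observed could differ, and those values still enter the primary analysis. It measures how much data the model omits, not a bias.

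None of this makes the specification usable. The protocol leaves technical detail to the SAP, so the SAP wording is what will be programmed. In an open-label trial, a time point settled at analysis is no longer prespecified. The remaining Week 24 analyses either reuse the imputation or address a different estimand.

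**Conclusion.** The concern holds. As written, the MMRM in SAP 3.2.3 cannot estimate the Week 24 treatment difference, and nothing else in that section repairs it. One of the two prespecified sensitivity analyses of the non-inferiority claim therefore does not address the primary endpoint. Week 18 results would be indirectly informative, but they are not a check of the Week 24 conclusion.

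The effect is confined to this analysis: the primary analysis, type I error, power and sample size do not change. The estimability result follows from the listed model terms alone and needs no assumption about the data. Only the count of about 522 unused values depends on an assumption, that the planned 10% dropout equals the proportion without a Week 24 HbA1c. No numerical effect on the trial's conclusion can be derived from the documents.

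**What to change.** In SAP 3.2.3, extend the visit factor to Weeks 8, 12, 18 and 24, so that the treatment-by-visit and baseline-by-visit terms also cover Week 24. State that the LS means difference, standard error, 95% confidence interval and non-inferiority p-value are taken from the treatment contrast at Week 24. Add the same statement to SAP 3.2.4, which lists the right visits but also names no week for its reported contrast.

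This is a wording change of a line or two, to be made before the analysis is run. It needs no new data and no change to the sample size, and it brings SAP 3.2.3 into agreement with SAP 3.2.1, SAP 3.2.4 and protocol 9.3.2.

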3.2.4 Supplementary analyses

Secondary estimand 1

Under hypothetical strategy, measurements after treatment discontinuation and/or initiation of rescue medication will be considered as missing data.

A MMRM, under the missing at random framework, will be performed based on ITT population. The model will include treatment, previous OADs, visit (Week 8, Week 12, Week 18 and Week 24), treatment-by-visit interaction as fixed effects, baseline HbA1c value-by-visit interaction as continuous covariate. The randomization stratum of HbA1c will be removed from the MMRM model given that the baseline HbA1c continuous value is already in the model. The MMRM model will be implemented using SAS® (Version 9.4 or higher) MIXED procedure (PROC MIXED) with an unstructured correlation matrix to model the within-participant errors. Parameters will be estimated using the restricted maximum likelihood method with the Newton-Raphson algorithm. Denominator degree of freedom will be estimated using the Kenward-Roger approximation by fitting values from post-randomization scheduled visits. LS Means difference between treatments, SE, 2-sided 95% CI, and 2-sided nominal non-inferiority p-value from MMRM will be provided.

Secondary estimand 2

For the per protocol estimand, the change in HbA1c from baseline to Week 24 will be analyzed using an ANCOVA with treatment group and previous OADs as fixed effects, and baseline HbA1c continuous value as covariate. Provided that participants with treatment discontinuation or rescue medication, as well of participants with missing assessment will be excluded from PP population, no missing data handling method is planned for this analysis. LS Means difference between treatments, SE, 2-sided 95% CI, and 2-sided nominal non-inferiority p-value from ANCOVA will be provided.

3.3 SECONDARY ENDPOINT(S) ANALYSIS

The secondary endpoints detailed in this section are key secondary efficacy endpoints and other secondary efficacy endpoints. Secondary safety endpoints analyses are defined in [Section 3.6.2](#) (AE, SAE, AESIs, AEs leading to treatment discontinuation, hypoglycemia), and [Section 3.6.3.1](#) (vital signs, safety laboratory values).

3.3.1 Key secondary efficacy endpoints

3.3.1.1 *Definition of endpoints*

The key secondary efficacy endpoints are:

- 2a The absolute change from baseline to week 24 in HbA1c.
- 2b The absolute change from baseline to week 24 in body weight.
- 2c Proportion of participants reaching HbA1c<7% at week 24.
- 2d Proportion of participants reaching HbA1c targets <7% without body weight gain at Week 24.
- 2e Proportion of participants reaching HbA1c <7% with no body weight gain at Week 24 and no hypoglycemia (defined as ADA level 1, 2 or 3) during treatment.

3.3.1.2 *Main analytical approach*

Key secondary efficacy endpoint 2a

If the primary objective is met, the key secondary efficacy endpoint 2a will be analyzed with the primary estimand defined the same as the primary estimand of the primary endpoint, except that 2-sided 97.5% CI and superiority p-value from ANCOVA will be provided if endpoint is to be tested as per the gate-keeping procedure defined in [Section 3.5](#); otherwise, 95% CI will be provided and no p-value will be provided.

Key secondary efficacy endpoint 2b

The key secondary efficacy endpoint 2b will be analyzed with the primary estimand defined according to the following attributes

- Endpoint: Change in body weight from baseline to Week 24.
- Treatment condition: iGlarLixi will be compared to IDegAsp.
- Analysis population: All randomized participants
- Intercurrent events (IE):
 - Treatment discontinuation IE will be handled with the treatment policy strategy: the endpoint will be assessed based on all assessments irrespective of the treatment discontinuation
 - The initiation of rescue medication IE will be handled with the treatment policy strategy: the endpoint will be assessed based on all assessments irrespective of the treatment discontinuation
- Population-level summary: LS Means difference between treatments from ANCOVA with treatment group, randomization stratum of HbA1c and previous OAD and baseline body weight as covariates. SE, 2-sided 97.5% CI and superiority p-value from ANCOVA will be provided if endpoint is to be tested as per the gate-keeping procedure defined in

[Section 3.5](#); otherwise, 95% CI will be provided and no p-value will be provided. Missing data will be imputed by multiple imputations using missingness patterns based on treatment completion, and under the missing at random (MAR) assumption within each pattern. The same imputation method as of the primary estimand of the primary endpoint will be used.

Descriptive statistics for body weight and changes from baseline will be provided for baseline and each visit by treatment group. Mean changes from baseline with the corresponding standard error will be plotted over time.

Key secondary efficacy endpoint 2c, 2d, and 2e

The key secondary efficacy endpoints 2c, 2d, and 2e will be analyzed with the primary estimand defined according to the following attributes:

- Treatment condition: iGlarLixi will be compared to IDegAsp.
- Analysis population: All randomized participants
- Intercurrent events (IE):
 - Treatment discontinuation IE will be handled with the treatment policy strategy: the endpoint will be assessed based on all assessments irrespective of the treatment discontinuation
 - The initiation of rescue medication IE will be handled with the treatment policy strategy: the endpoint will be assessed based on all assessments irrespective of the initiation of rescue medication
- Population-level summary: Odds ratio between treatments from logistic regression model adjusting for treatment group, randomization stratum of previous OADs, and appropriate baseline covariates. The proportion of participants in each treatment group will be provided, as well as the odds ratio between groups (HbA1c and body weight will be included as baseline continuous covariates when considered in the definition of endpoints). If an endpoint is to be tested as per the gate-keeping procedure defined in [Section 3.5](#), 2-sided CI at the specified significance level and the associated p-value will be provided; otherwise, 95% CI will be provided and no p-value will be provided. For the categorical secondary endpoints in which HbA1c is assessed at Week 24, all values at Week 24 will be used to determine whether a participant is a responder or not, even if they are measured after IMP discontinuation or introduction of rescue therapy. If no assessment is available at Week 24, participants will be treated as non-responders.

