 - For change in FPG, 7-point SMPG and fasting C-peptide from baseline to Week 24: LS Means difference between treatments from ANCOVA with the same analysis approach as of the primary estimand of the primary endpoint, except that the baseline of each endpoint will be included in the model rather than baseline HbA1c. Descriptive statistics for results and changes from baseline will be provided for baseline and each visit by treatment group. Mean changes from baseline with the corresponding standard error will be plotted over time. For 7-point SMPG, the average and each time point will be analyzed.
 - For total insulin dose in each group at week 24: LS mean difference between treatments, as well as SE and 2-sided 95% CI, from MMRM with treatment, randomization stratum of HbA1c, randomization stratum of previous OADs, visits and treatment-by-visit interaction as fixed effects. Descriptive statistics for percentage change from starting dose will be provided. Raw data and changes from starting dose with the corresponding standard error will be plotted over time.
 - For binary endpoints: Odds ratio between treatments from logistic regression model adjusting for treatment group, randomization stratum of previous OADs, baseline continuous HbA1c and appropriate baseline covariates. The proportion of participants in each treatment group will be provided, as well as the odds ratio between groups with associated 2-sided 95% CI. For the categorical secondary endpoints in which HbA1c is assessed at Week 24, all values at Week 24 will be used to determine whether a participant is a responder or not, even if they are measured after IMP discontinuation or introduction of rescue therapy. If no assessment is available at Week 24, participants will be treated as non-responders.

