4 SAMPLE SIZE DETERMINATION

A total sample size of 580 participants (randomization ratio 1:1, ie, 290 per intervention group) will be determined to demonstrate noninferiority of iGlarLixi versus IDegAsp in HbA1c reduction at Week 24 with 90% power and 2-sided significance level of 0.05 based on the following assumptions on the primary endpoint:

- True mean difference of zero between iGlarLixi and IDegAsp
- Common standard deviation of 1.05%
- Non-inferiority margin on the mean difference of 0.3%
- Dropout rate of 10%

Calculations were made based on two sample t-test using SAS® (Version 9.4).

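### For body weight (2b), the return-to-baseline fallback draws its noise from the between-person baseline SD, which overstates the standard error and can cost power if the fallback applies

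*SAP*

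**What the plan says.** SAP 3.2.2 handles treatment discontinuers without a Week 24 HbA1c by imputing from retrieved dropouts. If either arm has fewer than 10 of these, or the model fails to converge, it switches to return-to-baseline. The missing value is then drawn from a normal distribution centred on the participant's own baseline, with a "standard deviation based on the baseline value by treatment group". Protocol 9.3.2 has the same rule without the threshold of 10. The draw is repeated 1000 times and the results are combined by Rubin's rule.

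For the change in body weight (2b), SAP 3.3.1.2 specifies an ANCOVA that includes baseline weight and adds: "The same imputation method as of the primary estimand of the primary endpoint will be used". It names no weight-specific SD. For FPG, 7-point SMPG and fasting C-peptide, SAP 3.3.2.2 prescribes "LS Means difference between treatments from ANCOVA with the same analysis approach as of the primary estimand of the primary endpoint", with the baseline of each endpoint replacing baseline HbA1c.

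Under SAP 3.5, 2b is tested at two-sided 0.025 and is one of the two routes to 2d. The documents give no baseline weight SD, SD of weight change, expected weight difference or power for 2b.

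**The concern.** The natural reading of the rule is the SD of baseline values across the people in an arm. Once a draw is centred on someone's own baseline, the spread between people is already accounted for. What remains is how far one person's Week 24 value may stray from that baseline, which is a residual SD. Using the baseline SD counts between-person spread twice.

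For HbA1c this hardly shows, because the two SDs are of similar size. Body weight differs: adults vary by far more than one adult's weight changes in 24 weeks. Followed as written, the rule would give a participant who is meant to have returned to baseline a weight change of the order of the spread between participants. 2b is confirmatory, so a real weight difference could fail its test, and the reported interval would partly reflect how varied the enrolled population is.

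**Working it through.** **The plan's own figure.** The inputs in SAP section 4 are "A total sample size of 580 participants (randomization ratio 1:1, ie, 290 per intervention group) will be determined", "with 90% power and 2-sided significance level of 0.05", "True mean difference of zero between iGlarLixi and IDegAsp", "Common standard deviation of 1.05"% and "Non-inferiority margin on the mean difference of 0.3"%, with 10% dropout. Then n = 2 × 1.05² × (1.960 + 1.282)² / 0.3² ≈ 258 per arm (259 by the t-test). Dividing by 0.9 gives 287 (288), against the stated 290. The figure reproduces, but it concerns HbA1c only.

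**Inputs for 2b.** From the documents: n = 290 per arm and two-sided alpha 0.025 (critical value 2.241). Assumed: baseline weight SD S = 10–15 kg; SD of change s = 3–3.5 kg, also used as the residual SD; true difference d = 1, 1.5 or 2 kg. The share m of each arm imputed by the fallback is varied from 2.5% to 10%. The top value is the whole planned dropout with nobody retrieved.

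**Formulas.** The noise enters Rubin's variance within and between imputations:

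- Reported variance: T = (2/n)[(1 − m)s² + 2mS²]. The residual-SD rule replaces S with s.
- The estimate centres on (1 − m)d with variance of about (2/n)(1 − m)s², because 1000 imputations average the noise out.
- Power = Φ{[(1 − m)d − 2.241√T] / √[(2/n)(1 − m)s²]}.

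**One case in full** (m = 7%, s = 3, S = 12, d = 1):

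- Residual-SD rule: T = (2/290)(8.37 + 1.26) = 0.0664, SE 0.258; power = Φ[(0.93 − 0.578)/0.240] = 93%.
- Rule as written: T = (2/290)(8.37 + 20.16) = 0.197, SE 0.444; power = Φ[(0.93 − 0.994)/0.240] = 39%.

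A simulation of the full imputation and ANCOVA gave SEs of 0.258 and 0.445, and power of 92% and 42%.

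**SE ratio over the range.** For m from 3% to 10%, the ratio of the two SEs runs from 1.19 (m = 3%, S = 10, s = 3.5) to about 2.3 (m = 10%, S = 15, s = 3).

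**Chance that the fallback applies.** Retrieved dropouts per arm are taken as Binomial(290, stop rate × retrieved rate), and the trigger probability is 1 − (1 − P[≤ 9])². For 10% stopping and 30% retrieved, P[≤ 9] = 0.6275, so the probability is 1 − 0.3725² = 86%. Retention also sets m, so the two must be read together:

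| Stop treatment | Of these retrieved | Imputed (m) | Fallback applies | SE ratio | Power at 1 kg: residual SD → as written |
|---|---|---|---|---|---|
| 10% | 30% | 7% | 86% | 1.39–2.03 | 82–93% → 15–58% |
| 5% | 50% | 2.5% | 96% | 1.16–1.47 | 86–95% → 61–88% |
| 10% | 50% | 5% | 16% | 1.30–1.81 | 84–94% → 31–73% |
| 10% | 70% | 3% | under 1% | 1.19–1.55 | 86–95% → 54–85% |

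The ranges cover S = 10–15 kg and s = 3–3.5 kg. Power is conditional on the fallback applying.

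**Larger effects.** At 1.5 kg with m = 7%, power as written is 73–98%. It is halved only near m = 10% and S = 15 kg (44–49% against 99% or more). At 2 kg with m = 10%, it stays at 93% or above.

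**HbA1c.** With an assumed baseline SD of 0.7–1.0% and 5–10% imputed, the same rule gives an SE of 0.087–0.091. That compares with 1.05 × √(2/261) = 0.092 for 261 completers per arm, so the primary analysis is essentially untouched.

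**The case against.** The strongest reply is that the error is conservative. An overstated standard error cannot create a false superiority claim. If 2b fails, 2d can still be tested at 0.025 through 2a and 2c. SAP 3.3.1.3 also plans an MMRM of weight that does not use this imputation. All of this stands, although the MMRM is supplementary, targets a hypothetical-strategy estimand and cannot rescue the confirmatory test.

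The second reply is that the damaging branch may never be reached. The protocol asks discontinuers to stay in the study to its scheduled end (section 1.3 footnote d, section 7.1.1). The Week 24 window in SAP Appendix 4 is open-ended from Day 147 and accepts premature end-of-treatment values. With 70% retrieval the fallback is very unlikely. When few people stop it is likely, but then few values are imputed. This also stands: the documents give no retrieval rate, so they do not show the fallback to be the probable branch.

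Third, a reader might infer that the rule simply halves the power of 2b, or that it puts 10–15 kg of noise into the estimate. The documents support neither. The kilogram figures are assumptions, the loss depends on a true difference near 1 kg, and the noise averages out of the estimate. Return-to-baseline does shrink the estimate by a factor (1 − m), but it does so whatever SD is chosen.

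**Conclusion.** The point holds as a should-fix. The wording of SAP 3.2.2, carried into 3.3.1.2, counts between-person spread twice, and that conclusion needs no assumed number. Its size does. With a baseline SD of 10–15 kg, an SD of change of 3–3.5 kg and 3–10% imputed, the reported standard error for 2b is about 1.2 to 2.3 times what it should be whenever the fallback applies. Serious loss of power needs three things together: the fallback is triggered, several percent of each arm are imputed, and the true difference is near 1 kg. The documents do not settle any of the three. Neither the primary HbA1c conclusion nor type I error is at risk. The carry-over to FPG, SMPG and C-peptide has the same form, but its size was not calculated, and those endpoints lie outside the alpha-controlled family.

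**What to change.** In SAP 3.3.1.2, state that when return-to-baseline applies to 2b, the Week 24 weight is drawn from a normal distribution centred on the participant's own baseline weight. Its SD should be the residual SD given baseline, that is, the root mean square error of the Week 24 ANCOVA among participants of that arm with an observed Week 24 weight. Say explicitly that the SD of baseline weights is not used. Put the same endpoint-specific wording in 3.3.2.2, and in 3.2.2 for consistency, where it changes almost nothing.

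In simulations with a 1 kg difference, a 3.5 kg SD of change and a 12 kg baseline SD, using the SD of change as the noise raises power from 16% to 79% at 10% imputed and from 51% to 85% at 5%. Complete data would give 88%.

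The cost is a sentence or two in the SAP, with no effect on data collection or participants. It should be done before database lock, because a later change could look driven by the result.
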